5.13.2.4 Other Supportive Care

Bisphosphonates and RANK-L inhibitors are allowed for osteoporosis.

Live/attenuated vaccines are not allowed prior to or during the study. Vaccination with inactivated viruses is permitted consistent with the institutional guidelines. Allow appropriate time interval between the most recent study treatment administration and the next date of study treatment. If the patient experiences side effects after the flu vaccine or another inactivated vaccine, please manage study treatment administration per protocol guideline.

5.13.3 Prohibited and/or Restricted Concomitant Medications

5.13.3.1 Prohibited Medications

- Immunosuppressive agents
- Immunosuppressive doses of systemic corticosteroids (except as stated in Section 5.13.2) defined as a daily dose of greater than 10 mg prednisone equivalents
- Any concurrent systemic antineoplastic therapy for the treatment of melanoma or a new malignancy (except as noted). Patients who develop a new non-melanoma fully resectable malignancy (examples include but are not limited to: in situ bladder cancer, in situ gastric cancer, or in situ colon cancers; in situ cervical cancers/dysplasia; or breast carcinoma in situ; or prostate carcinoma) during the study may continue receiving study drugs if the only therapy required is hormonal therapy, surgery and/or radiation (and the surgery or radiation site does not overlap with a previous primary melanoma or melanoma metastasis location). Consultation with the Medical Monitor is required once a new malignancy is detected.
- Any live / attenuated vaccine (e.g., varicella, zoster, yellow fever, rotavirus, oral polio, and measles, mumps, rubella or Flumist® Quadrivalent) during treatment and until 100 days post last dose of nivolumab. Note: All vaccines available as of the date of this document against severe acute respiratory syndrome coronavirus 2 (SARS-CoV-2; COVID-19) are allowed on treatment. For any questions about COVID vaccines, please contact the Medical Monitor.

5.13.3.2 Blood Pressure Medications

Consideration should be given to withholding antihypertensive medications including diuretics, as well as other drugs with hypotensive properties (e.g., alpha blockers for benign prostatic hyperplasia), particularly when therapy involves multiple antihypertensive drugs and classes other than thiazide diuretics. If withholding antihypertensive medications, withhold no less than 12 hours and no more than 48 hours prior to each dose of bempegaldesleukin. Patients who are on medications with antihypertensive effects for the treatment of coronary artery disease (CAD) (e.g., β -blockers, Ca channel blockers, nitrates, etc.) should be able to withhold these drugs prior to initiation of treatment. Other medications (e.g., for erectile dysfunction) may also increase risk of hypotension; for further guidance on the continued use of these concomitant medications in patients treated with bempegaldesleukin, please consult the Medical Monitor.

Antihypertensive medications may be reinstated in between doses of bempegaldesleukin at any time as clinically indicated (e.g., based on blood pressure monitoring results).

In patients receiving β -blockers, consider a step-wise tapering of doses before initiation of bempegaldesleukin to avoid reflex tachycardia. If Grade ≥ 2 hypertension is observed in any cycle, patients should be monitored more frequently (at least weekly until a new stable antihypertensive regimen is identified). Patients may be monitored more frequently at the discretion of the Investigator as clinically warranted.

5.14 Adverse Events

All AEs, either reported by the patient or observed by study staff, will be recorded 100 (± 7) days after the last dose of all study treatment(s) (Safety Follow-up Visit 2) (Table 4, Section 8.5). This study will use the Medical Dictionary for Regulatory Activities for coding all AEs. AEs will be summarized by preferred term, system organ class, grade of severity, and relationship to each study drug (bempegaldesleukin and/or nivolumab).

5.15 Treatment Assignment and Patient Number Assignment

Each patient will be assigned a unique patient number after signing the ICF. Patient numbers will be used on all patients' study information. Patient numbers will not be reassigned.

An IRT will be employed to manage patient randomization and drug supply.

6.0 INVESTIGATIONAL PRODUCTS/STUDY DRUGS

6.1 Bempegaldesleukin (NKTR-214)

6.1.1 Drug Description and Formulation

[REDACTED]

[REDACTED]

6.1.2 Drug Packaging and Labeling

[REDACTED]

Each vial will be labeled with the study drug number/name, strength, name of the Sponsor, storage condition, lot number, and the required cautionary statement.

6.1.3 Drug Reconstitution and Handling

Instructions for reconstitution and handling of bempegaldesleukin (NKTR-214) drug product are provided in the Pharmacy Manual.

6.1.4 Drug Storage

Bempegaldesleukin drug product should be stored in a secure, locked area within temperature range, as specified on the drug label and [Table 7](#).

6.1.5 Drug Shipment

For all countries, Nektar will supply bempegaldesleukin and nivolumab from a central source. Refer to the Pharmacy Manual for additional details.

6.2 Nivolumab Preparation, Storage, and Packaging

Refer to the Pharmacy Manual for details.

6.3 Study Drug Accountability and Reconciliation

Bempegaldesleukin and nivolumab are considered Investigational Medical Products and will be supplied to the Investigator by Nektar Therapeutics or its designee. Depending on source of supply, the packaging and labeling will vary. Products will be labeled to meet local country requirements. Please refer to the Pharmacy Manual for details.

Study drug supplies must be kept in an appropriate, secure, locked area and stored in accordance with the conditions specified on the labels. Depending on local health authority guidelines, IV fluids and associated supplies (IV administration sets, calibrated pumps) may be obtained through commercial supply, the site pharmacy, or through a central depository.

The Investigator, pharmacist, or designee must maintain an accurate record of dispensing the study drug in a Drug Accountability Log, a copy of which must be given to Nektar Therapeutics.

The Drug Accountability Log may record specifics to study drug dispensation such as:

- Records of product delivery, inventory, temperature monitoring, destruction, and return as per Sponsor's instructions.
- Doses prepared, time prepared, doses dispensed.
- Doses and/or vials destroyed.

The Drug Accountability Log will be reviewed by the monitor during site visits and at the completion of the study.

7.0 ASSESSMENT OF EFFICACY

7.1 Imaging Assessments for the Study

Images will be submitted to an imaging core laboratory on an ongoing basis until BICR-confirmed distant recurrence. Sites should be qualified prior to scanning the first patient and understand the image acquisition guidelines and submission process as outlined in the Study 20-214-29/CA045-022 Imaging Manual provided by the imaging core laboratory.

Screening and follow-up images should be acquired as outlined in Section 1.2 (Schedule of Events). Radiographic tumor assessments will continue to be collected every 12 weeks (± 7 days) for up to 24 months from the date of randomization and then every 6 months (± 4 weeks) for up to 5 years (60 months) from the date of randomization until investigator-assessed and BICR-confirmed distant recurrence.

- For non-radiological recurrence, results of the biopsy confirming recurrence will be sent to the imaging core laboratory.
- For radiologic recurrence confirmed by biopsy, results will also be sent to the imaging core laboratory.

Tumor assessments at other time points may be performed if clinically indicated and should be submitted to the imaging core laboratory as soon as possible. If a patient starts systemic therapy for a new non-melanoma tumor after study drug discontinuation, follow-up scans can be done as per standard of care. Unscheduled imaging (CT/MRI, bone scan, and/or positron emission tomography [PET] scan) should be submitted to imaging core laboratory. An ultrasound of the sentinel-node basin and fluorodeoxyglucose (FDG)-PET should be submitted to the imaging core laboratory if recurrence was initially detected using either method and confirmed at a later time.

Clinical data, including stage information and primary site of disease, will also be submitted to the imaging core laboratory (e.g., details regarding surgery, biopsy, and procedures).

7.2 Definitions

Recurrence:

Recurrence is defined as the appearance of one or more new melanoma lesions, which can be local, regional, or distant in location from the primary resected site, based on modified criteria from RECIST version 1.1 ([Eisenhauer, 2009](#)):

- The finding of a new lesion should be unequivocal (i.e., not attributable to differences in scanning technique, change in imaging modality or findings thought to represent something other than tumor). If a new lesion is equivocal, for example because of its small size, continued therapy and follow-up evaluation will clarify if it represents truly new disease. If subsequent or repeat scans confirm there is definitely a new lesion, then recurrence should be declared using the date of the initial scan.

- If new lesions are identified by ultrasound in the course of the study, confirmation by biopsy or by CT or MRI should be performed and the results shared with the BICR (if so, the date of recurrence will be the date of the initial ultrasound). Suspected new pathological lymph nodes must be either ≥ 10 mm the short axis on CT or MRI or confirmed as recurrent disease by biopsy.
- FDG-PET scanning may be used to complement CT scanning in assessment of possible recurrence. If the positive FDG-PET at follow-up corresponds to a new site of disease confirmed by CT or MRI, this is disease recurrence. If the positive FDG-PET at follow-up is not confirmed as a new site of disease on CT or MRI, additional follow-up CT or MRI scans are needed to determine if there is truly progression occurring at that site (if so, the date of recurrence will be the date of the initial abnormal FDG-PET scan and the results shared with the BICR). A biopsy to confirm recurrence is strongly advised if safe to do so for recurrences initially identified by FDG-PET.

Local Recurrence:

Local cutaneous recurrence after adequate excision of the primary melanoma is associated with aggressive tumor biologic features and is frequently a harbinger of metastases. It is generally accepted that local recurrences occur within 2 cm of the tumor bed.

Regional Recurrence:

The neoplastic nature of the regional recurrences should be confirmed by histology/cytology.

- In-Transit Metastases: The AJCC defines in-transit metastases as any skin or subcutaneous metastases that are > 2 cm from the primary lesion but are not beyond the regional nodal basin. In-transit metastases occur in 10% to 15% of patients with Stage III disease. When present, in-transit metastases are usually multiple, evolve over time, and are often the harbinger of subsequent systemic disease.
- Regional Node Recurrences: Regional node failure in a previously dissected basin is usually found at the periphery of the prior surgical procedure.

Distant Recurrence:

Melanoma is well known for its ability to metastasize to virtually any organ or tissue. The most common initial sites of distance metastases are the non-visceral (skin, subcutaneous tissue, and lymph nodes), which are recurrence sites for 42% to 59% of subjects in various studies. Visceral locations are the lung, brain, liver, gastrointestinal tract, and bone; the visceral sites are the initial sites of relapse in approximately 25% of all melanoma patients who experience recurrence.

Distant metastases may be measurable or non-measurable.

Note:

- Cutaneous relapses occurring beyond the periphery of the previous surgical bed (i.e., > 2 cm) are considered distant metastases.
- Node relapses occurring beyond the anatomical compartment of the dissected basins are considered distant metastases.
- Node relapses in nodal basins situated in a different anatomical compartment or beyond the previously dissected basin or in two nodal basins (even if contiguous; i.e., 2 pelvic nodal basins, 2 mediastinal nodal basins) are considered distant metastases.

Date of Recurrence:

The first date when recurrence was observed is taken into account regardless the method of assessment. Therefore, recurrence will be declared for any lesion when:

- Only imaging was performed and recurrence confirmed
- Only pathology was done and malignancy confirmed (in solitary or in doubtful lesions, cutaneous, subcutaneous or lymph node lesions)
- Both pathology and imaging were done and recurrence/malignancy confirmed. In this case, the date of whichever examination comes first is considered the date of recurrence.

Results of biopsies confirming recurrence should be sent to the imaging core laboratory.

Note: for documentation, the date of recurrence is the date that the pathology and/or imaging confirms recurrence--not the date that the information was communicated to the patient.

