	Day 1 (≤ 5 days post-randomization)	Day 3 (-1 day)	Day 5 (± 1 day)	Day 8 (± 1 day)	Day 1 (± 3 days)	Day 4 (± 1 day) (call or visit)	
Efficacy Assessments							
Imaging Assessment	
Every 12 weeks (± 7 days) for up to 24 months from the date of randomization and then every 6 months (± 4 weeks) for up to 5 years (60 months) from the date of randomization; see Section 7.3 for additional details:
 
 • CT (contrast-enhanced preferred, unless contraindicated) of chest and CT or MRI (contrast-enhanced preferred, unless contraindicated) of abdomen, pelvis, and all other known sites of resected disease • Ultrasound of sentinel-node basin • Brain imaging for patients with baseline history of treated brain lesions: Brain MRI (without and with contrast; head CT with contrast allowed if patient develops contraindication for MRI) on the same schedule as other imaging • Brain imaging for patients without baseline history of brain metastases: Brain MRI (without and with contrast; head CT with contrast allowed if MRI contraindicated) annually from the date of randomization and as clinically indicated 
Notes:
 
 - Imaging assessment schedule is relative to the date of randomization and will be maintained regardless of dose delays or study drug discontinuation. - Use same imaging method as was used at Screening/Baseline - Continue imaging assessments until investigator-assessed and BICR-confirmed distant recurrence as defined in Section 7.1. 						

BICR = blinded independent central review; CRF = case report form; CT = computed tomography; CVA = cerebrovascular accident; EORTC QLQ-C30 = 30-item European Organisation for Research and Treatment of Cancer Core Quality of Life Questionnaire; EQ-5D-5L = European Quality of Life – 5 Dimensions Health State Classifier to 5 Levels; HCG = human chorionic gonadotropin; IV = intravenous; MRI = magnetic resonance imaging; PK = pharmacokinetic; WOCBP = women of childbearing potential.

a. Assessments and visits that occur outside of protocol-specified windows (e.g., for holidays, travel issues, insurance issues) may be acceptable on a case-by-case basis after review by the Medical Monitor.

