2.2.6 Rationale for Primary Endpoint (RFS) and Key Secondary Endpoints (OS and DMFS)

After complete surgical resection, there is no measurable disease to follow and recurrence is detected with surveillance scans, both during the treatment period for adjuvant therapy and afterwards until recurrence is documented. RFS in melanoma is a clinically meaningful endpoint, which is associated with OS and is the primary endpoint for this study. There are a number of marketed treatment regimens in the metastatic setting that are known to improve OS. Although post study treatment may confound the assessment of OS, OS has been the gold standard for demonstrating clinical benefit for cancer drugs and is a key secondary endpoint for this trial.

Although any recurrence (i.e. local, regional, or metastatic) is accounted for in RFS, it is clinically meaningful to determine the time to distant metastasis, which directly impacts OS. In other words, since a local recurrence or a regional recurrence can be treated with curative intent by appropriate surgical intervention and possibly further adjuvant systemic treatment, distant metastasis is incurable and more directly correlates with OS. Therefore, DMFS by Investigator, defined as the time from randomization until first occurrence of distant metastasis or death, is another key secondary endpoint of the study.

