9.4.2 Secondary Endpoints

Secondary endpoints are presented in [Table 15](#).

Table 15: Secondary Endpoints

Endpoint	Description
OS	Defined as the time between the date of randomization and the date of death due to any cause. Patients who do not have a date of death will be censored on the last date for which a patient was known to be alive. Evaluated in the ITT population.
DMFS by BICR	Defined as the time between the date of randomization and the date of first distant metastasis by BICR or date of death due to any cause, whichever occurs first. For patients who remain alive and distant metastasis-free, DMFS will be censored on the date of last disease assessment. DMFS will be evaluated in patients who are Stage III at study entry.
DMFS by Investigator	Defined as the time between the date of randomization and the date of first distant metastasis by Investigator or date of death due to any cause, whichever occurs first. For patients who remain alive and distant metastasis-free, DMFS will be censored on the date of last disease assessment. DMFS will be evaluated in patients who are Stage III at study entry.
PFS2	PFS2 is defined as time from randomization to progression per Investigator after the start of next line of therapy or death, whichever occurs first. Patients who were alive and without progression after the next line of therapy can be censored at last known alive date. Evaluated in the ITT population. Details on the PFS2 analysis will be described in the SAP.
Overall Safety and Tolerability	Measured by the incidence of adverse events, serious adverse events, deaths, and laboratory abnormalities in the safety population.

Table 15: Secondary Endpoints (Cont'd)

Endpoint	Description
PROs	Measured by (group-level and individual-level) changes from baseline in scores for the GH/QoL and physical functioning subscales of the EORTC QLQ-C30 questionnaire.
PD-L1 Expression as a Predictive Biomarker for RFS	Measured by the RFS by BICR endpoints based on PD-L1 expression level.
RFS by Investigator	Defined similar to the primary endpoint, but recurrence and new primary melanoma are decided by Investigator.

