WOCBP = women of childbearing potential.

Laboratory tests must be assessed by a local laboratory within 24 hours, or as soon as locally feasible, prior to each bempegaldesleukin and/or nivolumab study drug administration.

**APPENDIX 2: AMERICAN JOINT COMMITTEE ON CANCER DEFINITIONS
FOR T, N, M STAGING AND PROGNOSTIC STAGE GROUPS**

Definition of Primary Tumor (T)^a

T Category	Thickness	Ulceration Status
TX: Primary tumor thickness cannot be assessed (e.g., diagnosis by curettage)	Not applicable	Not applicable
T0: No evidence of primary tumor (e.g., unknown primary or completely regressed melanoma)	Not applicable	Not applicable
Tis (melanoma in situ)	Not applicable	Not applicable
T1	≤ 1.0 mm	Unknown or unspecified
T1a	< 0.8 mm	Without ulceration
T1b	< 0.8 mm	With ulceration
	0.8–1.0 mm	With or without ulceration
T2	> 1.0–2.0 mm	Unknown or unspecified
T2a	> 1.0–2.0 mm	Without ulceration
T2b	> 1.0–2.0 mm	With ulceration
T3	> 2.0–4.0 mm	Unknown or unspecified
T3a	> 2.0–4.0 mm	Without ulceration
T3b	> 2.0–4.0 mm	With ulceration
T4	> 4.0 mm	Unknown or unspecified
T4a	> 4.0 mm	Without ulceration
T4b	> 4.0 mm	With ulceration

AJCC = American Joint Committee on Cancer; T = tumor.

- a. The original and primary source for this information is the AJCC Cancer Staging Manual, eighth edition (2017) published by Springer International Publishing (modified from: Gershenwald JE, Scolyer RA, Hess KR, et al. Melanoma of the skin. In: Amin MB, Edge SB, Greene FL, et al, eds. AJCC Cancer Staging Manual. 8th ed. New York: Springer International Publishing; 2017:563–585).

Source: [Gershenwald, 2017 \(Table 2\)](#)

Definition of Regional Lymph Node (N)^a

Extent of Regional Lymph Node and/or Lymphatic Metastasis		
N Category	No. of Tumor-Involved Regional Lymph Nodes	Presence of In-Transit, Satellite, and/or Microsatellite Metastases
NX	Regional nodes not assessed (e.g., sentinel lymph node [SLN] biopsy not performed, regional nodes previously removed for another reason); Exception: pathological N category is not required for T1 melanomas, use clinical N information	No
N0	No regional metastases detected	No
N1	One tumor-involved node or any number of in-transit, satellite, and/or microsatellite metastases with no tumor-involved nodes	
N1a	One clinically occult (i.e., detected by SLN biopsy)	No
N1b	One clinically detected	No
N1c	No regional lymph node disease	Yes

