N2	Two or 3 tumor-involved nodes or any number of in-transit, satellite, and/or micro- satellite metastases with one tumor-involved node	
N2a	Two or 3 clinically occult (i.e., detected by SLN biopsy)	No
N2b	Two or 3, at least one of which was clinically detected	No
N2c	One clinically occult or clinically detected	Yes
N3	Four or more tumor-involved nodes or any number of in-transit, satellite, and/or microsatellite metastases with 2 or more tumor-involved nodes, or any number of matted nodes without or with in-transit, satellite, and/or microsatellite metastases	
N3a	Four or more clinically occult (i.e., detected by SLN biopsy)	No
N3b	Four or more, at least one of which was clinically detected, or the presence of any number of matted nodes	No
N3c	Two or more clinically occult or clinically detected and/or presence of any number of matted nodes	Yes

AJCC = American Joint Committee on Cancer; N = node.

- a. The original and primary source for this information is the AJCC Cancer Staging Manual, eighth edition (2017) published by Springer International Publishing (modified from: Gershenwald JE, Scolyer RA, Hess KR, et al. Melanoma of the skin. In: Amin MB, Edge SB, Greene FL, et al, eds. AJCC Cancer Staging Manual. 8th ed. New York: Springer International Publishing; 2017:563–585).

Source: [Gershenwald, 2017 \(Table 3\)](#)

Definition of Distant Metastasis (M)^a

M Category ^b	M Criteria	
	Anatomic Site	LDH Level
M0	No evidence of distant metastasis	Not applicable
M1		
M1a	Distant metastasis to skin, soft tissue including muscle, and/or nonregional lymph node	Not recorded or unspecified
M1a(0)		Not elevated
M1a(1)		Elevated
M1b	Distant metastasis to lung with or without M1a sites of disease	Not recorded or unspecified
M1b(0)		Not elevated
M1b(1)		Elevated
M1c	Distant metastasis to non-CNS visceral sites with or without M1a or M1b sites of disease	Not recorded or unspecified
M1c(0)		Not elevated
M1c(1)		Elevated
M1d	Distant metastasis to CNS with or without M1a, M1b, or M1c sites of disease	Not recorded or unspecified
M1d(0)		Not elevated
M1d(1)		Elevated

AJCC = American Joint Committee on Cancer; CNS = central nervous system; LDH = lactate dehydrogenase; M = metastasis.

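### Section 7.2 makes a skin relapse more than 2 cm beyond the primary's surgical bed, but inside the regional nodal basin, both regional and distant, so DMFS has no single event rule for it

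*Protocol*

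**What the plan says.** Protocol Section 7.2 sorts recurrences into local, regional and distant. Local recurrence is taken to lie within 2 cm of the tumour bed. In-transit metastases are listed under Regional Recurrence and described, with attribution to AJCC, as "any skin or subcutaneous metastases that are > 2 cm from the primary lesion but are not beyond the regional nodal basin". The Note under Distant Recurrence then says "Cutaneous relapses occurring beyond the periphery of the previous surgical bed (i.e., > 2 cm) are considered distant metastases". The Note sets no outer limit and makes no exception for in-transit disease.

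DMFS depends on the regional/distant boundary. Table 15 in Section 9.4.2 counts the "first distant metastasis by Investigator or date of death due to any cause, whichever occurs first", with a parallel definition by BICR, both in patients who are Stage III at entry. Section 2.2.6 states that "DMFS by Investigator, defined as the time from randomization until first occurrence of distant metastasis or death, is another key secondary endpoint". SAP 4.2 and 6.11.2.2 repeat the event definition. None of these places refers to Section 7.2 or says how in-transit skin disease is to be counted.

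Imaging depends on the same boundary. Tables 2 to 4 instruct sites to "Continue imaging assessments until investigator-assessed and BICR-confirmed distant recurrence as defined in Section 7.1".

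**The concern.** An endpoint needs one rule for what counts as an event. Here two sentences in one section give opposite answers for the same lesion, so DMFS event status, and with it the event or censoring date, depends on which sentence the assessor applied.

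With early termination the SAP drops DMFS by BICR and keeps DMFS by Investigator. The class assigned at the open-label site is therefore the only one left, and different sites could have applied different sentences without departing from the protocol.

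The Note also sits uneasily with other parts of the protocol. Section 2.2.6 justifies DMFS by contrasting distant metastasis with earlier relapse, "since a local recurrence or a regional recurrence can be treated with curative intent by appropriate surgical intervention". Appendix 2 places in-transit disease in the N category (N1 is "One tumor-involved node or any number of in-transit, satellite, and/or microsatellite metastases with no tumor-involved nodes"), and M1a is "Distant metastasis to skin, soft tissue including muscle, and/or nonregional lymph node", with no 2 cm rule. Appendix 2 is cited for staging at entry, so it does not decide which sentence governs DMFS.

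**Working it through.** **Do the two sentences overlap?**

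| | In-transit bullet (regional) | Note (distant) |
|---|---|---|
| Lesion type | skin or subcutaneous | cutaneous |
| Inner limit | > 2 cm from the primary | > 2 cm beyond the previous surgical bed |
| Outer limit | not beyond the regional nodal basin | none |
| DMFS event? | no | yes |

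Take a cutaneous relapse more than 2 cm beyond the bed of the excised primary. It is necessarily more than 2 cm from the primary. If it is also within the basin, it satisfies every condition in both columns. Purely subcutaneous lesions, and lesions within 2 cm of the bed, are not clearly affected. Where the previous surgical bed is not that of the primary, the overlap is less certain, so the finding is limited to the primary's bed.

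**Does any other text settle it?** The DMFS definitions (synopsis, Sections 2.2.6 and 9.4.2, SAP 4.2 and 6.11.2.2) use distant metastasis without further definition. Section 7.1 gives the imaging schedule and stopping point, and cites the Imaging Manual for acquisition and submission. No precedence rule was found.

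**How much does one patient matter?** The plan gives no figure to reproduce. Inputs:

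- About 774 patients enrolled (SAP 5.1), randomised 1:1.
- 12-month RFS of 70.5% assumed for nivolumab (protocol Section 9.2).

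Per arm, N is at most about 774 / 2 = 387. This is an approximate ceiling. Section 5.2 uses enrolment from consent, before randomisation, and the SAP analysis covers only treated patients who were Stage III at entry.

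- *Crude event proportion.* For a patient whose event status changes: 1 / 387 = 0.258%, about 0.26 points. At the planned 475 per arm it would be 1 / 475 = 0.21 points.
- *Kaplan-Meier rate at time t, relapse at s < t, patient otherwise event-free and followed past t.* The shift is at least 1/N, about 0.26 points, with equality when nobody is censored before t.
- *Same, but the patient is otherwise censored at s.* Counting the event multiplies S(t) by 1 − 1/n(s), where n(s) is the number at risk. The shift is S(t)/n(s), at least 0.705 / 387 = 0.18 points at 12 months. This assumes 12-month DMFS is no lower than the planning RFS of 70.5%. Distant metastases and deaths are a subset of RFS events, but the 70.5% is a nivolumab-arm planning value applied here to both arms.
- *Relapse after 12 months.* Neither reported rate moves.

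If the patient later has an undisputed distant metastasis or dies, the change is mainly in the event date rather than in event status.

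**How many patients?** This cannot be derived. Section 7.2 says in-transit metastases occur in 10% to 15% of Stage III patients. That figure includes subcutaneous lesions and is not an on-study relapse rate, so no count is taken from it.

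**The case against.** The strongest reply is that the sentences are not of equal standing. The in-transit bullet reports an AJCC definition and goes on to incidence and prognosis, as background would, while the Note uses operative language. On that reading the Note is the study rule. This is a fair reading. But the bullet stands under the study's own Regional Recurrence heading, and nothing says the Note overrides it. If it did, almost no cutaneous disease would remain in the in-transit category.

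The second reply is that little is at stake. The trial has ended, no between-arm comparison will be made, and DMFS was never formally tested. That stands, and it limits the weight of the point. It does not remove it, because the SAP still reports DMFS by Investigator by arm.

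The third is that the SAP can be run as written by taking the investigator's recorded class, and that re-deriving an investigator endpoint afterwards in an open-label study carries its own risk. The analysis can indeed be run, but a reader would not know what the recorded class means for these lesions. A both-readings summary should therefore supplement the recorded class, not replace it.

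Two caveats also stand. No case report form is in the documents, so the site detail needed to reclassify may not exist. And the per-patient figures are approximate, since 774 is a rounded count and the arms need not be equal.

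**Conclusion.** The contradiction is real and unresolved. For cutaneous relapses more than 2 cm beyond the primary's surgical bed and inside the regional basin, the protocol gives two opposite DMFS classifications and no precedence. This should be fixed before DMFS is reported.

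Its reach is narrow. RFS counts local, regional and distant recurrence alike, and only RFS by BICR and OS were to be formally tested, so RFS, OS and error control are untouched. The total effect on DMFS is unknown. The per-patient effects of about 0.26 and 0.18 points are lower bounds under the stated assumptions (no more than about 387 per arm and, for the second, 12-month DMFS of at least 70.5%). They do not show that a reported rate would change materially.

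Scheduled imaging is affected only where investigator and BICR both called the relapse distant. How often that happened cannot be seen from the documents.

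**What to change.** 1. **Section 7.2.** Reconcile the two sentences and state which governs. Limiting the Note to relapses beyond the regional nodal basin would agree with Appendix 2 and Section 2.2.6. The alternative is to say expressly that the Note overrides the in-transit bullet. The sponsor should say which was intended.
2. **SAP 6.11.2.2.** State the chosen rule for DMFS by Investigator. Alongside the summary of the investigator's recorded class, report event counts and 6- and 12-month rates under both readings where the recorded site allows. List the patients whose class changes or cannot be determined.
3. **Tables 2 to 4 (optional).** Section 7.1 holds the imaging rule, but distant recurrence is defined in Section 7.2, so a pointer there would help.

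The cost is one precedence sentence, one SAP rule, one repeated summary and one listing, plus three cross-references if the optional item is taken up. The derivation work depends on how much site detail was recorded. Imaging already stopped cannot be recovered. For those patients the regional reading censors at the last disease assessment, so the two readings compare an event with a censoring at about the same date.
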